(6) - Secukinumab 300 mg at Week 0, 1, 2, 3, 4, 8 (and 12 and Q4W)	Secukinumab
(2) - M1095 30 mg at Week 0, 2, 4, 8 (2a) and Q4W if no escalation at Week 12 (2b) and M1095 120 mg Q4W if escalation at Week 12	30mg (x4), Q4
(3) - M1095 60 mg at Week 0, 2, 4, 8 (3a) and Q4W if no escalation at Week 12 (3b) and M1095 120 mg Q4W if escalation at Week 12	60mg (x4), Q4
(4) - M1095 120 mg at Week 0, 2, 4, 8 (and 12 and Q8W)	120mg (x4), Q8
(5) - M1095 120 mg Q2W at Week 0, 2, 4, 6, 8, 10 (and 12 and Q4W)	120mg (x6), Q4
	Total M1095 ^c

a: Subjects will be assigned to a treatment group based on the actual treatment they received most during the overall period for all treatment groups except for (1), (2b) and (3b). Regarding (2b) and (3b), subjects will be assigned to a treatment group based on the actual treatment they received most during the induction period.

b: Plac/120 mg (x4), Q4 include all subjects who were mostly administered M1095 120 mg from Week 12 to Week 44 having received placebo during the induction period. The data will only be presented from Week 12 onwards for this treatment group.

c: Total M1095 will include all subjects who received M1095 at any time during the study i.e. (1), (2), (3), (4) and (5).

All pairwise treatment comparisons will be two-sided at the 5% level, without adjustment for multiplicity unless otherwise specified.

All primary/secondary efficacy and exploratory QoL endpoints will be presented in tables including visits from Week 0 to Week 52 as follows: 0, **1, 2, 3, 4, 6, 8, 10, 12**, // 14, 16, 20, **24**, // 28, 32, **36**, 40, 44, **48** and 52 (each week number, written in bold, indicates the weeks, at which the pairwise treatment comparisons will be made and // indicates the boundary for the study periods). In regard to interim analyses, only visits up to Week 12 will be included for IA1. IA2 will include data up to Week 24 for all subjects and beyond Week 24 for some subjects depending on the cut-off date (see Section 2). The analyses may be split by period or by combined periods depending on the tables produced for IA1 and IA2.

For all efficacy and quality of life analyses unless specified otherwise, baseline will be defined as the last non-missing assessment prior to the first dose of study medication (planned at Week 0).

For safety analyses, baseline will be defined differently according to the treatment period:

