4.7.1 Variables

Treatment exposure will be characterized by the following variables:

- the duration of study exposure that corresponds to the period from the date of the first dose of study drug to either the date of last study visit (Week 52) for the subjects who completed the study or the date of discontinuation for subjects who discontinued during the study,
- the duration of treatment exposure in days and in subject-years including the duration of dose hold in days for the response assessment/dose hold period (subject-years is calculated by adding the number of subjects in the group and multiplying that number by the years that subjects were on treatment),
- the frequency of treatment exposure determined by the number of injections received,
- the actual amount/dose in mg received by the subjects as well as the percentage of the scheduled dose that was actually received,

Treatment compliance will also be described with:

- the number and proportion of subjects receiving the complete dose as scheduled,
- the number and proportion of subjects that are compliant and non-compliant in each treatment group.

For the induction and maintenance/escalation periods, the duration of treatment exposure is the difference in days between the date of last study visit in the considered treatment period unless subjects have discontinued during this period and the date/time of the first dose of study drug in the same period.

Exposure $_{[\text{period } x]} = \text{last study visit date }_{[\text{period } x]} - 1^{\text{st}} \text{ study drug dose date/time }_{[\text{period } x]}$.

For subjects who have discontinued from placebo at or prior to the last visit of the induction period, the duration of exposure will be the sum of the number of days between the date/time of the first dose and the date of treatment discontinuation.

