For subjects who have discontinued from M1095/Secukinumab treatment at or prior to the last visit of the induction or maintenance/escalation periods, the duration of exposure will be the sum of the number of days between the date/time of the first dose in the considered period and the date of the last dose before discontinuation and 56 days that correspond to the longest period of washout for M1095/Secukinumab. If the study discontinuation occurred within the 56 days after the last dose received, the duration of exposure will be defined as the difference in days between the date of study discontinuation and the date of first dose of study drug.

Exposure $_{[\text{period } x]} = \text{last dose date/time }_{[\text{period } x]} - 1^{\text{st}} \text{ study drug dose date/time }_{[\text{period } x]} + 56 \text{ days}$.

The treatment exposure of response assessment/dose hold period will be described by several variables:

- the number of subjects who have dose of study drug being withheld at Week 24,
- the duration in days of the dose being withheld during the period i.e. the difference in days between the date of the visit at Week 24 and the date/time of M1095 re-commencement,
- the total duration in days of the dose being withheld since the last dose of M1095 i.e. the difference in days between the date of the last dose of study drug before dose of Week 24 being withheld i.e. at Week 20 and the date/time of M1095 re-commencement (see Table 4.12).

The duration of exposure to M1095/secukinumab treatment overall during the combined induction, maintenance/escalation and response assessment/dose hold periods be calculated as follows:

Secukinumab: Exposure $_{[\text{overall}]} = \text{date/time of last dose} - \text{date/time of } 1^{\text{st}} \text{ dose} + 56 \text{ days}$.

M1095: Exposure $_{[\text{overall}]} = \text{date/time of last dose} - \text{date/time of } 1^{\text{st}} \text{ dose} - d_1 + 56 \text{ days}$.

with the date/time of the first dose as described in Table 4.12 for the different treatment groups and subtracting the dose hold duration for the overall period while considering the 5 half lives of the M1095 treatment (d_1) as explained in Table 4.12. This duration will also be expressed in subject-years by adding the amount of times in days that subjects spent on treatment for all subjects divided by the total number of days in a year i.e. 365.25.

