 - If the partial or complete start and end dates do not indicate as to when the AE started and ended compared to the first dose of study drug of any period, the AE will be flagged on-treatment for all periods.
- If both start and end dates are both missing: the AE will be considered on-treatment and therefore a TEAE for all periods.

To determine the worsening of an AE during study treatment, the maximum severity for each AE during the baseline period will be considered. In case of missing severity, the conservative approach below will be followed:

- If an AE has a missing severity during the study treatment, it will be defined as treatment-emergent.

- If the severity of an AE is missing at baseline and this event continues during the study treatment, this AE will be considered as treatment-emergent.

Adverse events of Special Interest (AESI) include cytopenias, liver function test changes/enzyme elevations, infections, injection-site reactions, allergic/hypersensitivity reactions, cerebrocardiovascular events, malignancies, depression, Crohn's disease and ulcerative colitis. Additional adverse events may be identified as being of special interest during the study and prior to first unblinding.

An overview table will present the number and percentage of subjects experiencing these types of AEs below by treatment:

- TEAEs,
- TEAEs by relationship to investigational product,
- serious TEAEs including deaths,
- TEAEs by maximum severity,
- deaths,
- and TEAEs leading to study treatment discontinuation.

This table will be produced for all separate treatment periods and the overall periods (refer to Table 4.3, Table 4.13, Table 4.14 and Table 4.15).

For the overall period, the exposure-adjusted incidence per 100 subject-years will also be presented. The exposure-adjusted incidence will be calculated by dividing the number of subjects with AEs by the total person years of exposure during the treatment period (refer to Section 4.7). This result will be multiplied by 100 to obtain the exposure-adjusted incidence per 100 subject-years.

The AESI will also be displayed with an overview table by treatment for each treatment period and the overall periods.

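### The overall-period exposure-adjusted AE incidence keeps counting exposure after a subject's first event, so for common categories it still depends on length of follow-up

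*SAP*

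**What the plan says.** SAP 4.9.2.5 adds one rate to the AE overview table: "For the overall period, the exposure-adjusted incidence per 100 subject-years will also be presented". It is obtained by "dividing the number of subjects with AEs by the total person years of exposure during the treatment period", times 100, with exposure taken from Section 4.7. The overview rows are any TEAE, TEAEs by relationship, serious TEAEs, TEAEs by maximum severity, deaths, and TEAEs leading to discontinuation.

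SAP 4.7.1 sets overall M1095 exposure at last dose minus first dose, minus a hold term d1, plus 56 days. Secukinumab has the same formula without d1. The hold term comes from "subtracting the dose hold duration for the overall period while considering the 5 half lives of the M1095 treatment"; Table 4.12 makes it d − 56 days, or zero if that is negative. Subject-years come from "adding the amount of times in days that subjects spent on treatment for all subjects", divided by 365.25. Earlier in the same section there is a different formula: "subject-years is calculated by adding the number of subjects in the group and multiplying that number by the years that subjects were on treatment".

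No step ends a subject's exposure at the first AE, and no rate of events per subject-year is specified.

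The columns differ in planned length. For Plac/120mg, Table 4.3 footnote b says: "The data will only be presented from Week 12 onwards for this treatment group". In Table 4.13, subjects escalated at Week 12 give Weeks 0 to 12 to the 30 mg or 60 mg column and later data to the pooled 120 mg column. The overall TEAE window in 4.9.2.5 runs from first dose to 8 weeks after the last dose and does not leave out hold time. The same section rules out imputing partial or missing AE dates.

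**The concern.** An exposure adjustment is there so that columns followed for different lengths can be compared. A subject who has had the event cannot add to the numerator again, yet here goes on adding to the denominator. The result is not a first-event rate. At a constant hazard it falls as follow-up lengthens, so part of the imbalance stays in the figure.

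No formal safety comparison is planned (SAP 4.9, Protocol 9.4.5), so readers will compare the printed rates by eye. For a common category, a column with shorter follow-up would look somewhat worse at the same risk, and a real difference could look smaller, or sometimes larger, than it is.

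**Working it through.** The documents state no AE rate, so there is no planned figure to reproduce. AE frequencies below are assumptions, shown as a range.

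**Inputs**
- Last dose at Week 44 (Protocol 6.7) and a 56-day tail (SAP 4.7.1).
- Dosed from Week 0, completer, no hold: 44 × 7 + 56 = 364 days.
- Plac/120mg from Week 12: 32 × 7 + 56 = 280 days. The ratio is 280/364 = 0.769.

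**Formulas.** With constant first-event hazard L and exposure T:
- SAP formula: (1 − exp(−LT)) / T, which falls as T grows.
- Time cut at first event: (1 − exp(−LT)) / [(1 − exp(−LT)) / L] = L, for any T.

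**Equal risk, unequal follow-up.** Let p be the share with an event by 364 days, counted here as one year, so L = −ln(1 − p). Rates are per 100 subject-years.

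| p | L (cut at first event) | SAP, 364 days | SAP, 280 days | Spurious ratio |
|---|---|---|---|---|
| 5% | 5.1 | 5.0 | 5.0 | 1.01 |
| 20% | 22.3 | 20.0 | 20.5 | 1.03 |
| 50% | 69.3 | 50.0 | 53.7 | 1.07 |
| 70% | 120.4 | 70.0 | 78.5 | 1.12 |
| 80% | 160.9 | 80.0 | 92.3 | 1.15 |

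Example for 70%: (1 − exp(−1.204 × 0.769)) / 0.769 = 0.785. At 5% the printed level is 5.0/5.13 = 0.975 of the first-event rate, a 2.5% shift.

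**Real difference, equal follow-up.** Take 60% against 80% at one year. The rate ratio is ln(0.2)/ln(0.4) = 1.76. The SAP formula gives 0.80/0.60 = 1.33, which is the crude risk ratio.

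**Real difference, unequal follow-up.** Use 280 and 364 days over 365.25 (0.767 and 0.997 years), with comparator L = 1 per year and a true ratio of 1.2. If the 280-day column has the higher hazard, the printed ratio is 1.24. If the 364-day column has it, the printed ratio is 1.00. The error can go either way.

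**Dose hold.** A hold from Week 24 with restart at Week 36 gives d = (36 − 20) × 7 = 112 and d1 = 112 − 56 = 56, hence 364 − 56 = 308 days of exposure. An AE starting in those 56 subtracted days still lies in the TEAE window. If 40% of a column were held this way, mean exposure would be 364 − 0.4 × 56 = 341.6 days. At equal hazard the printed rate would exceed secukinumab's by 364/341.6 = 1.07. Assumed extremes:
- 20% held, restart at Week 32 (d1 = 28): 364/358.4 = 1.02.
- 60% held, restart at Week 44 (d1 = 112): 364/296.8 = 1.23.

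This mismatch is separate from the first-event problem and would remain if only that were corrected.

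**The case against.** Several points on the other side stand.

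- The rate is planned only for the overall period and sits beside numbers and percentages. The text does not attach it to the AESI overview or to the SOC/PT tables. A reader might infer that it is the main cross-arm safety comparison. The documents do not support that: the randomised placebo comparison is the induction period, tabulated separately over a common 12 weeks, and no hypothesis or decision rule uses this figure.
- The adjustment does most of its job for uncommon events. Under the same model, the 280-day to 364-day ratio at equal risk is 0.77 for the crude percentage and 1.01 for the SAP figure at 5% incidence, and 0.79 against 1.03 at 20%. Only for very common events is the gain largely lost (0.86 against 1.12 at 70%).
- A reader might infer that between-arm ratios are always understated. That is assured only at similar exposure; the case of 1.2 printing as 1.24 shows the opposite.
- At equal follow-up the printed ratio is the one-year risk ratio, a legitimate measure, although a table headed as a rate per 100 subject-years does not tell the reader so.
- The two subject-years formulas do not leave the overall denominator undefined. The summed-days definition is explicit for that period, and the looser parenthetical needs only an editorial correction.

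None of this alters the defining sentence: subjects are counted once, and their exposure runs on.

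**Conclusion.** The point holds for common categories, chiefly any TEAE. At equal risk the 280-day column prints about 7% to 15% above a 364-day column when 50% to 80% have an event by one year. At similar exposure true rate ratios are compressed (1.76 prints as 1.33); at unequal exposure they may be over- or understated. Categories at 5% or less move by about 2% to 3%.

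These sizes rest on a constant hazard, completers only, no dose hold, and event frequencies that the documents do not give. With holds, M1095 exposure shortens further, and the mismatch between the TEAE window and the denominator pushes M1095 rates upward. The effect is on how a descriptive safety table is read. No test and no efficacy conclusion changes. It is worth correcting because the change is small and lets the adjustment do what it is there for.

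**What to change.** In SAP 4.9.2.5, define the figure separately for each overview category: subjects with at least one such event, divided by the sum over subjects of exposure time (overall definition in 4.7.1) up to first onset of that category, or to the end of the TEAE window if there is none, times 100. Then:

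- **Dose hold.** State that hold time is handled alike in numerator and denominator. Either keep it in the denominator, or leave out AEs that start in the subtracted part.
- **Onset dates.** State a rule for this calculation only, as an explicit exception to the no-imputation sentence in 4.9.2.5. For a partial date, use the earliest possible date in the window. For AEs with wholly missing dates, state a separate convention and report how many subjects it affects; the earliest-date rule would give them almost no time at risk and raise the rate.
- **Subject-years.** In 4.7.1, delete the parenthetical that multiplies a number of subjects by years and keep the summed-days definition.

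The cost is a few lines of SAP text, one derived variable and a date convention. Printed rates will be higher, most visibly for any TEAE, so a table footnote should name the definition. Crude numbers and percentages stay as planned.

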4.9.2.6 Depression and Suicidality/Self-Injurious Behavior

Suicide-related thoughts and behaviors and self-injurious behavior with no suicidal intent based on the eC-SSRS, and depression based on the PHQ-8 will be listed by subject and visit up to Week 52.

In addition, the frequency and percentage of subjects with at least one post-baseline eC-SSRS assessment with suicidal ideation, suicidal behavior, suicidal ideation or behavior, treatment-emergent suicidal ideation and emergence of suicidal behavior will be summarized by treatment group (see Section 7.5 – Appendix E: Derivation of eC-SSRS for further information). The total PHQ-8 score and absolute change from baseline will be described by a by-treatment summary table for each visit (see Section 7.4 – Appendix D: Scoring of PHQ-8).

4.9.3 Graphical Presentation

Boxplots to visualize trends and data distributions in longitudinal continuous safety data (vital signs, ECG parameters, laboratory parameters) will be produced by treatment group and visit.

4.10 Pharmacokinetic (PK) Parameters

All subjects within the pharmacokinetic population will be included in the PK parameter analysis and may be reported in a separate report.

4.10.1 Variables

M1095 serum concentrations in ng/mL will be assessed at the following visits: Weeks 0, 2, 4, 8, 12, 24, 36, 44, 48 and 52.

4.10.2 Descriptive Analyses

Descriptive summary statistics of serum concentration will be provided for each treatment period by treatment sequence of the considered period and visit/sampling time point (the induction period summaries will present all treatment groups of Table 4.2 except for Secukinumab (6), Placebo (1) and total M1095, the maintenance/escalation period summaries will present all treatment groups of Table 4.14 in addition to Plac/120mg (x4), Q4, 30mg (x4), Q4/No Esc, 60mg (x4), Q4/No Esc, 120mg (x4), Q8, 120mg (x6), Q4, the response assessment/dose hold period summaries will present all treatment groups of Table 4.14 and Table 4.15). The summary statistics will include arithmetic and geometric means, SD, arithmetic and geometric CV, minimum, median, and maximum and the frequency (number of subjects and percentage) of concentrations below the LLOQ. All concentrations below LLOQ will be treated as zero in summary statistics for concentration data. The geometric mean will not be reported if the data include zero values. Serum concentrations will also be listed by treatment group, subject and visit/sampling time point. Graphical methods will be

employed to show the mean concentration-time plot and the individual concentration-time profiles by actual treatment group, with time defined as visit and actual day respectively.

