### 2.3 Benefit/Risk Assessment

Despite several biologic treatment options, new psoriasis therapies are needed. M1095 is a viable candidate treatment with the potential for a similar or improved risk/benefit profile compared to available therapies. All subjects in this study will receive M1095 or secukinumab as those randomized to placebo will switch to M1095 at Week 12.

In EMR200574-003, subjects received three doses of M1095 at 2-week intervals over one month. Dose levels of 30mg through 240mg were tested. The study demonstrated that

- M1095 administered up to a dose of 240mg q2w x 3 was generally well tolerated in a group of 33 subjects with moderate to severe psoriasis.
- AUC and Cmax were dose proportional from 30mg to 240mg with a terminal half life of 11-12 days.
- A dose-response relationship was observed with PASI 75/90/100 responses.

The most common AEs (occurring in 2 or more of the 33 subjects treated with M1095) were pruritus, headache, hypertension, nasopharyngitis, somnolence and bronchitis. Two subjects discontinued due to AEs (an injection site reaction in a subject receiving 120mg and an elevation in aminotransferases in a subject receiving 240mg) and one SAE occurred (acute vestibular syndrome, in a subject receiving 30mg, which was deemed unrelated to study drug).

Subjects in the study were between 18 and 70 years old with moderate to severe psoriasis of at least 6 months duration, a static Physician's Global Assessment (sPGA) of  $\geq 3$ ,  $\geq 10\%$  body surface area and a PASI score of  $\geq 12$ . PASI 75/90/100 responses at Week 12 (8 weeks after the last M1095 injection) ranged from 88%/50%/13% to 100%/100%/56%. Achievement of sPGA scores of 0 and 1 at week 12 ranged from 88% to 100%. A full description of the safety and efficacy data from this study can be found in the Investigator's Brochure.

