## 8.7 Pharmacokinetics

Pharmacokinetic samples will be collected at the timepoints specified on the SoA (Section 1.3).

Samples will be shipped initially to the study's central laboratory and tested by the sponsor or sponsor's designee.

Serum M1095 levels will be assessed at trough (i.e. before study drug is given) at the following visits: Weeks 0, 2, 4, 8, 12, 24, 36, 44, 48, 52 and Early Discontinuation. M1095 serum concentrations will be summarized at these timepoints.

Drug concentration information will not be reported to investigative sites or blinded personnel until the study has been unblinded.

Details of the analysis will be provided either in the Statistical Analysis Plan (SAP), or in a separate PK Plan, prior to the analysis taking place.

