| 
 • M1095 60 mg at weeks 0, 2, 4, 8, 12, and Q4W until Week 20 and Placebo Q4W* | } | if IGA _{Week12} ≤ 1 and IGA _{Week24} = 0 |
|--|---|--|
- | | | |
|--|---|--|
| 
 • M1095 30 mg at weeks 0, 2, 4, 8, 12 and Q4W | } | if IGA _{Week12} ≤ 1 and IGA _{Week24} > 0 |
|--|---|--|
- | | | |
|--|---|--|
| 
 • M1095 60 mg at weeks 0, 2, 4, 8, 12 and Q4W | } | if IGA _{Week12} ≤ 1 and IGA _{Week24} > 0 |
|--|---|--|
- | | | |
|---|---|------------------------------|
| 
 • M1095 30 mg at weeks 0, 2, 4, 8 and M1095 120 mg at week 12, and Q4W | } | if IGA _{Week12} > 1 |
|---|---|------------------------------|
- | | | |
|---|---|------------------------------|
| 
 • M1095 60 mg at weeks 0, 2, 4, 8 and M1095 120 mg at week 12, and Q4W | } | if IGA _{Week12} > 1 |
|---|---|------------------------------|
- | | | |
|---|---|------------------------------|
| 
 • M1095 120 mg at weeks 0, 2, 4, 8, 12 and Q8W until Week 20, and Placebo Q4W* | } | if IGA _{Week24} = 0 |
|---|---|------------------------------|
- | | | |
|--|---|------------------------------|
| 
 • M1095 120 mg at weeks 0, 2, 4, 6, 8, 10, 12 and Q4W until week 20, and Placebo Q4W* | } | if IGA _{Week24} = 0 |
|--|---|------------------------------|
- | | | |
|---|---|------------------------------|
| 
 • M1095 120 mg at weeks 0, 2, 4, 8, 12 and Q8W | } | if IGA _{Week24} > 0 |
|---|---|------------------------------|
- | | | |
|--|---|------------------------------|
| 
 • M1095 120 mg at weeks 0, 2, 4, 6, 8, 10, 12 and Q4W | } | if IGA _{Week24} > 0 |
|--|---|------------------------------|
- **Secukinumab 300 mg at weeks 0, 1, 2, 3, 4, 8, 12** and Q4W

*If the IGA score of these subjects subsequently increases to 1 or more at any time after Week 24, these subjects will be re-administered the study treatment M1095 at the dose they received prior to Week 24 on a Q4W regimen at the scheduled visits as per protocol until the end of the treatment period. Dose will not be withheld for a second time, irrespective of subsequent IGA scores.

Figure 1.1: Flow chart / Study Design Diagram

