(2) - M1095 30 mg at Week 0, 2, 4, 8 (and: (2a.i) Q4W and dose hold from Week 24)	Yes	30mg (x4), Q4/No Esc/Hold
(2a.j) Q4W)	No	30mg (x4), Q4/No Esc/No Hold
(2b) M1095 120 mg Q4W if escalation at Week 12)	N/A	
(3) - M1095 60 mg at Week 0, 2, 4, 8 (and: (3a.i) Q4W and dose hold from Week 24)	Yes	60mg (x4), Q4/No Esc/Hold
(3a.j) Q4W)	No	60mg (x4), Q4/No Esc/No Hold
(3b) M1095 120 mg Q4W if escalation at Week 12)	N/A	
(4) - M1095 120 mg at Week 0, 2, 4, 8 (and: (4.i) 12 and Q8W)	Yes	120mg (x4), Q8/Hold
(4.j) 12 and Q8W and dose hold from Week 24)	No	120mg (x4), Q8/No Hold
(5) - M1095 120 mg Q2W at Week 0, 2, 4, 6, 8, 10: (5.i) 12 and Q4W and dose hold from Week 24)	Yes	120mg (x6), Q4/Hold
(5.j) 12 and Q4W	No	120mg (x6), Q4/No Hold

*: Subjects will be assigned to a treatment group based on the actual treatment they received most during the induction, maintenance/escalation and response assessment/dose hold periods.

Note: Rows in grey will not be presented in tables.

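### From Week 36 the Hold rows of the PK summary can mix subjects still off drug with subjects restarted on q4w, so dose and restart proportion are confounded in the Hold means and mean plots

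*SAP*

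**What the plan says.** SAP 4.10.2 summarises serum M1095 by treatment sequence and visit. For the last treatment period, "the response assessment/dose hold period summaries will present all treatment groups of Table 4.14 and Table 4.15". Table 4.14 covers the escalated subjects. Table 4.15 gives every other M1095 arm one Hold row and one No Hold row, for example "120mg (x6), Q4/Hold". Its footnote reads: "Subjects will be assigned to a treatment group based on the actual treatment they received most during the induction, maintenance/escalation and response assessment/dose hold periods". That gives one group per subject for the whole period, and no row identifies a restart.

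Held subjects do not stay off drug together. At the first later visit with IGA of 1 or more, each is "re-administered the study treatment M1095 at the dose they received prior to Week 24 on a Q4W regimen" (SAP 1.4). This can happen at Week 28, 32, 36, 40 or 44, or never.

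SAP 4.10.1 fixes the sampling: "M1095 serum concentrations in ng/mL will be assessed at the following visits: Weeks 0, 2, 4, 8, 12, 24, 36, 44, 48 and 52". Protocol 8.7 makes these pre-dose samples. SAP 4.7.1 places the last active dose before the hold at Week 20, and Protocol 6.7 places the last study dose at Week 44.

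For PASI, SAP Table 4.9 does separate visits during the hold from visits after restart. SAP 4.10.2 has no such separation for concentrations.

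**The concern.** A mean concentration describes a regimen only if the subjects in the cell share that regimen. From Week 36 a Hold cell can hold two populations whose expected concentrations differ by about two orders of magnitude or more. Its mean then depends mainly on how many subjects have restarted, and this can differ between arms because restart depends on response. A comparison of Hold rows across doses would confound dose with restart proportion, and the mean plot would show neither washout nor recovery cleanly.

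Arm 4 has a labelling problem as well: subjects restarted every 4 weeks remain under a label that says Q8.

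The tables and mean plots of an exploratory analysis are at stake. Protocol 8.10.1 also relies on serum concentrations to interpret the antibody results, and for that it matters who was on drug at the sample.

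**Working it through.** **Inputs.** Half-life: the phase 1 study reported dose-proportional exposure "with a terminal half life of 11-12 days" (Protocol 2.3). Last dose before the hold: Week 20. PK visits after Week 24: Weeks 36, 44, 48 and 52, pre-dose. Assumptions: one-compartment (mono-exponential) decline, and a restart proportion *p* shown as a range because the documents do not give it.

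**The plan's own figure.** Protocol 8.5.4 equates 8 weeks with 5 terminal half-lives: 56 / 5 = 11.2 days, inside 11-12. This reproduces.

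**Time off drug if still held.** 36 − 20 = 16, 44 − 20 = 24, 48 − 20 = 28 and 52 − 20 = 32 weeks.

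**Decay factors.** r(d) = 2^(−d/h), with h = 11 and 12 days: r(28) = 0.171 and 0.198; r(56) = 0.029 and 0.039; r(84) = 0.005 and 0.008.

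**Week 24.** Every Hold subject is scheduled to be 4 weeks past Week 20 and the sample is pre-dose, so the row is not mixed.

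**Week 36.**
- Still held: r(84) = 0.5-0.8% of the Week 24 concentration.
- The q4w steady-state trough is r(28)/(1 − r(28)) per unit dose. For 120 mg this is 24.8 (h = 11) or 29.7 (h = 12) relative units.
- Restarted at Week 28 (two doses), 120 mg (x6) arm, residual included: 24.2/24.8 = 98% and 28.8/29.7 = 97%.
- Restarted at Week 32 (one dose): 20.7/24.8 = 83% and 24.0/29.7 = 81%.
- A subject restarting at Week 36 itself is still off drug at the sample.

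**Hold mean at Week 36.** Mean = p × C(restarted) + (1 − p) × C(held). Take the 120 mg (x6) arm with restarts split equally between Weeks 28 and 32 (assumption). C(restarted) is then 22.4 or 26.4, and C(held) is 0.13 or 0.24.

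| p | h = 11 | h = 12 |
|---|---|---|
| 0.2 | 4.6 | 5.5 |
| 0.5 | 11.3 | 13.3 |
| 0.8 | 18.0 | 21.2 |

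The mean is almost linear in p. Restarted subjects supply at least 92% of it at p = 0.1 and at least 99% at p = 0.5. The median switches from near zero to the restarted value as p passes 0.5.

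**Confounding with dose.** On the same assumptions, 30 mg Hold with p = 0.8 gives 4.5-5.3 and 120 mg (x6) Hold with p = 0.2 gives 4.6-5.5. A fourfold dose difference is hidden by the restart mix.

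**Week 52.** Restarted subjects are 56 days past the Week 44 dose. A subject at q4w steady state has fallen by a further factor r(28), to 17-20% of the q4w trough.

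**Arm 4.** Active doses without a hold fall at Weeks 20, 28, 36 and 44.
- Weeks 36 and 44 are 8-week troughs for the No Hold group. The steady-state q4w/q8w trough ratio is [r(28)/(1 − r(28))] / [r(56)/(1 − r(56))] = 1 + 1/r(28) = 6.8 (h = 11) and 6.0 (h = 12).
- At Weeks 48 and 52 both regimens were last dosed at Week 44, and the ratio is (1 − r(56))/(1 − r(28)) = 1 + r(28) = 1.17-1.20.

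**Row texts.** In Tables 4.10 and 4.15, row (4.i) is labelled Hold but its text mentions no hold, while (4.j) is labelled No Hold but its text carries the hold from Week 24. Table 4.12 has these two texts the other way round.

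**The case against.** The best defence is that little depends on these tables. The stated objective and endpoint are population PK (Protocol 3.0). That model is exploratory, can use each subject's own dosing dates, and may be specified in a separate PK plan and presented apart from the main study report (Protocol 9.4.7). SAP 4.10.2 itself also plans individual profiles by actual day, listings by subject and visit, the median and range, and the frequency of values below LLOQ. Unmixed regimen data are available from induction, from Week 24 and from the No Hold rows. All of this stands and limits the weight of the point. None of it changes the Hold means and mean plots that the SAP specifies.

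The defence also rules out several stronger readings that a reader might infer:
- That the Hold mean reflects restart proportion rather than exposure. Dose still scales the mean; it just cannot be separated from the restart mix.
- That washout and recovery are lost altogether. The individual profiles and listings show both.
- That restarted subjects are at steady state at every visit. The one-dose and Week 52 figures show otherwise.
- That the six- to sevenfold Arm 4 ratio applies throughout. It applies at two of the four visits.
- That the rule "The geometric mean will not be reported if the data include zero values" is an error. The documents give no LLOQ, the convention is disclosed, and the median and the frequency below LLOQ are still reported. A geometric mean of quantifiable values only would be biased upward in washed-out groups.

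**Conclusion.** The point holds for Weeks 36, 44, 48 and 52, and not for Week 24. The SAP's grouping lets a Hold cell contain both subjects 16 to 32 weeks off drug and re-dosed subjects. At Week 36 the two states differ about 100- to 190-fold across half-lives of 11-12 days and the arms calculated. The Hold mean is thus close to the restart proportion times a dose-scaled trough, and Hold rows cannot be compared across doses without knowing that proportion.

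The figures rest on the phase 1 half-life, one-compartment decline, scheduled dosing times and an assumed range of restart proportions. The existence of the mixing rests only on the SAP's grouping and restart rules. No efficacy conclusion is affected. This is a worthwhile correction to a descriptive, exploratory output, not a threat to the trial's main results.

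**What to change.** In SAP 4.10.2, for Weeks 36 to 52, present each Hold group and its mean concentration plot split by status at the sample: no M1095 dose since Week 24, or at least one restart dose given before the sample. This follows the separation already made for PASI in Table 4.9. Label restarted Arm 4 subjects as restarted on q4w. Show the number of subjects in each state at each visit, so that the restart proportion is visible. Reconcile the (4.i) and (4.j) row texts in Tables 4.10 and 4.15 before the groups are programmed. If a separate PK plan is to govern these displays, put the same split there and refer to it from the SAP.

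The cost is SAP wording and programming, because dosing dates and concentrations are already collected. Table 2.1 limits the second interim PK analysis to Week 24, so only the final outputs change. The downside is smaller cells, since each Hold group is a subset of about 50 randomised subjects. A further split by weeks off drug or number of restart doses would be too thin, and the individual profiles can serve that purpose.
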